### METHODS

**Overview:** A randomized, double-blind, placebo-controlled clinical trial among individuals (N=90) with SUD and PTSD will be conducted to test the hypothesis that N-acetylcysteine (NAC) will significantly reduce SUD severity, craving, and PTSD symptoms. A subset of enrolled subjects between the ages of 21-40 will complete neuroimaging procedures before and after treatment. All procedures will be reviewed by the MUSC IRB and the Ralph H. Johnson VA Research and Development committee prior to study start.

**Participants:** Ninety male and female participants between the ages of 18 to 75 with current AUD/SUD and comorbid PTSD or sub-threshold PTSD will be recruited to participate in the study.

**Recruitment:** Primary recruitment sites include (1) the Ralph H. Johnson VAMC outpatient Substance Treatment and Recovery Clinic (STAR) and (2) the PTSD Clinical Team (PCT).

**Inclusion/Exclusion Criteria:** To be included, subjects must (1) be 18-75 years old, (2) meet DSM-5 criteria for current PTSD or subthreshold PTSD, and (3) meet DSM-5 criteria for current AUD/SUD. Exclusion criteria include: (1) schizophrenia, bipolar disorder or an eating disorder; (2) any significant medical illness (e.g., asthma) that may adversely affect safety or study participation; (3) psychotropic medication initiation within 4 weeks of study participation or use of the following medications: carbamazepine, phenytoin, nitrous oxide, methotrexate, 6-azauridine triacetate, nitroglycerin or any other medication that may have an adverse interaction with NAC; (4) pregnant or nursing women; and (5) clinically significant suicidal ideation and intent.

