We plan to use REDCap for data capture and management. REDCap (Research Electronic Data Capture) is a software toolset and workflow methodology for electronic collection and management of research and clinical trial data (Harris et al., 2008; Harris et al., 2007). REDCap provides secure, web-based flexible applications, including real time validation rules with automated data type and range checks at the time of entry. Exports are made available for several statistical packages including SPSS, SAS, SATA, R and Microsoft Excel.

**Power and Sample Size Estimation.** It is expected that subjects treated with NAC, as compared to placebo, will exhibit significantly lower PTSD symptoms and craving at week 8. The effect sizes for these analyses ( $d = 1.27$ ,  $d = 1.03$ , respectively) are based on our PoP data. A sample size of 26 would provide power ( $1-\beta$ ) of .80 to detect a large effect size with a Type 1 error protection level of .05 (Cohen, 1988). It is expected that NAC, as compared to placebo, will exhibit significantly lower AUD/SUD severity at week 8. To date, no published studies have examined NAC for the treatment of AUD. Assuming a medium effect size ( $d = .2$ ), with a Type 1 error protection level of .05 and  $(1-\beta) = .80$ , a total sample of 58 would be required. Recent unpublished pilot data conducted by our group examining the effects of NAC vs. placebo on standard number of drinks among patients with cocaine dependence and comorbid AUD ( $n=28$ ) found a statistically significant treatment group effect. With regard to neuroimaging, a recent study of 29 individuals (PTSD=14, controls=15) observed significant differences in PFC-AMY resting state connectivity (Sripada et al., 2012). The effect size for this difference was 0.8 (Cohen's  $d$ ). Thus, power ( $1-\beta$ ) reaches .80 with a total sample size of  $N=26$  (two-tailed,  $\alpha = .05$ ). Another study of 45 cocaine-dependent individuals showed that lower PFC-AMY connectivity at baseline predicted relapse (McHugh et al., 2014). The effect size for this reduction was 1.0. Thus, power ( $1-\beta$ ) reaches .80 with  $N=34$  subjects (two-tailed,  $\alpha = .05$ ).

**Hypotheses:** The hypotheses and statistical approaches for testing each hypothesis are listed below.

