## Protocol: Glial Regulators for Testing Comorbid Posttraumatic Stress Disorder and Substance Use Disorders

total number of standard drinks consumed and the OCDS total score as the primary outcomes. A Poisson distribution will be assumed with a logarithm link function to assess the effects of NAC treatment. Data collected in substance abuse studies often contain a preponderance of zeros, and these zeros in the distribution can be considered sampling zeros in the Poisson process (Bandyopadhyay et al., 2011). If this excess is present in the distribution, two-part Hurdle models (Poisson and NB) will be explored (Cragg et al., 1971). The hurdle part of the model will allow us to estimate the probability of abstinence during the study period (as an odds ratio) while the Poisson/NB portion will allow for the assessment of the risk of an increase in using days beyond zero during the study period (as a risk ratio). Baseline alcohol/substance use and craving will be included in pertinent models as covariates. Additional alcohol/substance use outcomes will be assessed: change in percent drinking days, percent heavy drinking days, EtG, and VAS craving levels.

Hypothesis 2: NAC treatment will result in significantly greater reduction in PTSD severity (CAPS-5) as compared to placebo. To test this hypothesis, generalized linear mixed effects regression models with a Gaussian distribution will be developed to assess group differences while adjusting for baseline CAPS-5 scores. Assumptions of residual normality and homoscedasticity will be checked using statistical test and graphical methods (Residual and Q-Q plots, and Shapiro-Wilk tests) and transformation will be done as necessary. Restricted maximum likelihood methods will be used to estimate the fixed effects and variance components. Additional outcomes (e.g., PCL-5, CAPS-5 symptom subscales) will be examined.

Hypothesis 3A: Prefrontal cortex-amygdala connectivity at rest and in response to alcohol/drug vs. neutral cues will predict reduction in alcohol/substance use severity (total standard drinks).

Hypothesis 3B: Prefrontal cortex-amygdala connectivity at rest and in response to trauma vs. neutral cues will predict reduction in PTSD severity (CAPS-5).

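### The sample size of 58 for AUD/SUD severity follows from neither a medium effect nor d = .2; as a week-8 comparison these need 128 and 788

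*Combined protocol and SAP*

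**What the plan says.** The Power and Sample Size Estimation paragraph, under Statistical Analyses, expects that NAC, compared with placebo, "will exhibit significantly lower AUD/SUD severity at week 8". It continues: "Assuming a medium effect size ( $d = .2"), "with a Type 1 error protection level of .05" and power of .80, "a total sample of 58 would be required". For this figure it gives no test, sidedness, allocation ratio, number of repeated measures, within-person correlation or allowance for dropout.

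Elsewhere the plan sets enrolment: "A randomized, double-blind, placebo-controlled clinical trial among individuals (N=90) with SUD and PTSD will be conducted". The analysis text for Hypothesis 1 names total standard drinks as a primary outcome, to be analysed in a mixed-effects framework with a Poisson distribution and hurdle models if zeros are in excess. It adds: "Baseline alcohol/substance use and craving will be included in pertinent models as covariates". Table 1 schedules the Timeline Follow-Back weekly during treatment.

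**The concern.** The sentence has two faults. The first needs no calculation: the effect is labelled medium and valued at .2, and by the usual convention those are different sizes of d. The documents do not define medium numerically, so taking it as .5 is an assumption here. The same paragraph does cite the standard power-analysis text for its large effect.

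The second fault is that 58 is far too small for either reading of the comparison described, a difference between two groups at week 8 in d units.

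No other sample-size calculation covers this primary outcome. The pilot result mentioned next reports statistical significance but no effect size, so it cannot take its place. If 58 were right, N=90 would look comfortable. If it is not, the plan does not show which drinking effects N=90 can detect, and a non-significant result could be misread as evidence against a medium effect.

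**Working it through.** **Inputs.** From the power paragraph: d = .2 or medium (taken as d = .5), alpha .05, power .80, stated total 58. From the Methods overview: N=90. Assumed because the sentence does not say: two-sided test, 1:1 allocation, no attrition.

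**Method.** For a two-sample t-test with total N in equal arms, power comes from the noncentral t distribution with N − 2 degrees of freedom and noncentrality d√N / 2.

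**Check against the plan's own figures.** For the relapse study, the paragraph states that "The effect size for this reduction was 1.0" and gives N=34, two-tailed. At d = 1.0 the method also gives 34 (noncentrality 1.0 × √34 / 2 = 2.92).

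**Total needed for 80% power, and power at three totals**

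| d | Total for 80% | Power at 58 | Power at 90 | Power at 116 (58 per arm) |
|---|---|---|---|---|
| .2 | 788 | .116 | .155 | .187 |
| .4 | 200 | .322 | .467 | .570 |
| .5 | 128 | .465 | .650 | .761 |
| .75 | 58 | .80 | .94 | .98 |

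The d = .4 row covers the possibility that .2 was meant as Cohen's f, since d = 2f for two equal groups.

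**Detectable d at 80% power:** 0.75 with 58; 0.60 with 90; 0.63 with 81 (10% loss); 0.67 with 72 (20% loss); 0.52 with 116. The loss rates are illustrative.

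**Other readings of the sentence**
- *One-sided test:* 620 at d = .2 and 102 at d = .5.
- *58 per arm:* the text says total, 116 exceeds N=90, and power at 116 is still below .80 for both readings.
- *Baseline adjustment at a single visit:* the requirement is multiplied by 1 − r². Reaching 58 needs r = √(1 − 58/128) = .74 at d = .5, or √(1 − 58/788) = .96 at d = .2.

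**Planned structure: baseline adjustment and repeated visits.** The normal approximation is N = 4(1.96 + .8416)² v / d². With a common correlation r, v = 1 − r² for one visit and v = (1 + 7r)/8 − r² for the mean of 8 weekly values. Example: d = .5, r = .5, one visit gives 31.4 × .75 / .25 = 94. The values of r are assumed; totals are rounded to the nearest whole number.

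| | r = .3 | r = .5 | r = .7 |
|---|---|---|---|
| One visit, d = .2 | 714 | 589 | 400 |
| One visit, d = .4 | 179 | 147 | 100 |
| One visit, d = .5 | 114 | 94 | 64 |
| 8-visit mean, d = .2 | 234 | 245 | 194 |
| 8-visit mean, d = .4 | 58 | 61 | 49 |
| 8-visit mean, d = .5 | 37 | 39 | 31 |

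**Settings that do reach 58.** A group-by-time F test with f = .2, m = 3 measures and correlation .3 has noncentrality N f² m / (1 − r) = 58 × .04 × 3 / .7 = 9.94 and power .802. The mean of 8 visits at d = .4 and r = .3 also gives about 58. Each needs a different effect metric or a different quantity being compared, plus a correlation that the plan does not state.

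**The case against.** The strongest reply is that the figure is under-specified rather than wrong. The trial will analyse weekly drinking data with a baseline-adjusted mixed model, and some plausible repeated-measures settings give 58, including the 8-visit mean at d = .4 and r = .3. If .2 was Cohen's f mislabelled as d, the figure might have a legitimate origin. That is possible and cannot be excluded. It does not rescue the printed sentence, which is written in d, refers to week 8, calls .2 medium and states none of the inputs such a calculation needs.

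The paragraph also has no uniform method. For d = 0.8 it gives 26 as a total, whereas the t-test needs 52 in total, or 26 per arm. So agreement at d = 1.0 shows that the t-test matches one of the paragraph's calculations, not all of them. That mismatch is a separate fault, and reading 58 as per arm has been tested above and fails.

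Three limits stand. The documents do not say that N=90 was derived from 58. All the totals here are on the d scale; the power of the planned Poisson or hurdle model cannot be computed from the documents. And which effects a completed trial leaves open is judged from its confidence interval, not from planning power.

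**Conclusion.** The concern holds. For the comparison the sentence describes, 58 is too small by a factor of about 2.2 if medium (d = .5) is meant (128/58) and about 13.6 if d = .2 is meant (788/58). The 788 does not depend on how medium is defined; the 128 does. Both rest on a two-sided, 1:1, unadjusted t-test without attrition, and a one-sided test does not change the conclusion.

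This does not show that the trial needs 128 or 788 participants. With baseline adjustment, N=90 could suffice at d = .5: at one visit it falls short at correlations of .3 and .5 but not at .7, and averaging 8 weekly values brings the requirement well below 90. At d = .2 none of the settings tried comes below 194. Whether N=90 is adequate for a medium effect therefore depends on assumptions that the plan omits.

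**What to change.** First establish how 58 was obtained. If it came from a repeated-measures calculation, state the effect-size metric, the number of measures, the correlation and the contrast tested. If it cannot be traced, delete the claim that 58 suffices. In either case reconcile the word medium with the value .2.

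If 58 is withdrawn, a replacement could read:

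> Assuming 1:1 allocation, no attrition and an unadjusted two-sided comparison of means at week 8 (alpha .05), N=90 gives 80% power for d = 0.60, about 65% for d = .5 and about 16% for d = .2. The planned baseline-adjusted mixed model may have higher power, depending on the correlations assumed.

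Then state those correlations, the allocation ratio and the expected attrition, and note that the benchmark is on the d scale and does not represent the count model. A remark that a non-significant drinking result would not exclude small, and possibly medium, effects is useful but optional.

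The cost is protocol wording. The correction itself adds no enrolment and changes no endpoint or model, though the stated power may become less favourable.

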### **Associated Areas of Functioning**

- Deployment Risk and Resiliency Inventory-2 (DRRI-2): The DRRI-2 (Vogt et al., 2012) is a suite of 17 individual scales that assess key deployment-related risk and resilience factors with demonstrated implications for Veterans' long-term health. The following subscales will be used to assess deployment factors: Combat Experiences. We will use the Post-Deployment Life Events and Support scales to evaluate post-deployment factors for Veterans.
- CNS Vital Signs Cognitive Testing: A battery of two tests (Stroop & Shifting Attention) will assess neurocognitive functions.

**Compensation:** Participants will be compensated \$50 for the baseline visit, \$50 for each imaging visit, \$40 for each completed weekly visit, and \$75 for completing each of the follow-up visits. They will be given a \$25 bonus if the baseline/first visit is attended as scheduled. Participants who previously consented to the optional neuropeptide Y will receive \$15 compensation for completing the second blood draw. Thus, participants may receive up to \$755 for completing all visits. Compensation is available in the form of cash, gift card, or check.

Telehealth participants will be offered compensation for travel to and from the three mandatory in-person visits (Baseline, Week 4, & Week 8).

**Neuroimaging Component:** Given the severe negative outcomes associated with co-occurring AUD/SUD and PTSD and lack of effective treatments, investigation of the neural circuitry and neurochemistry underlying AUD/SUD/PTSD and involved in positive therapeutic response could be important in guiding future treatment development studies. To that end, fMRI and H-MRS data will be acquired at baseline and end of treatment on a subset (n=40) of participants to examine (a) glutamate concentrations, (b) resting state connectivity, and (c) response to alcohol/drug, trauma, and neutral cues. Scans will be conducted at the MUSC Center for Biomedical Imaging.

The neuroimaging component will involve three visits, each lasting 60-90 minutes. During visit 1, we will develop the personalized imagery scripts for alcohol/drug, trauma, and neutral cues. During visit 2 (pre-treatment) and visit 3 (end of treatment), we will conduct the fMRI and H-MRS scanning procedures. Imagery scripts will be similar to those developed according to standardized procedures (Sinha & Li, 2007) and employed in our ongoing research.

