## Protocol: Glial Regulators for Testing Comorbid Posttraumatic Stress Disorder and Substance Use Disorders

Following auto-shimming, single-voxel water-suppressed  $^1\text{H}$ -MRS spectra will be acquired using a Point Resolved Spectroscopy (PRESS) sequence: Repetition Time (RT) = 2000ms; Echo Time (TE) = 40ms; number of averages = 128; an unsuppressed water spectrum will be co-acquired (TE = 40ms, number of averages = 16), scaled for partial volume effects and relaxation, and used as a concentration reference (Mullins et al., 2008).

Participants will be asked to relax and keep their eyes opened and fixed on a cross-hair for two six-minute runs while resting state data are collected. Following this, participants will be exposed to alcohol/drug, trauma and neutral cues, which will be audio recorded descriptions of the most recent time they used alcohol/drug, details of a traumatic event, and details about a relaxing event.

We will use a block design consisting of a single run in which 4 task blocks alternate with rest blocks. The 4 task blocks consist of a neutral cue followed by a trauma cue followed by a neutral cue then an alcohol/drug cue. To minimize potential carry-over effects, the order of task blocks will be counterbalanced so that half of the subjects in the placebo group and half of the subjects in the NAC group are exposed to the alcohol/drug cue first and the remaining participants in each group are exposed to the trauma cue first. This order will be repeated at the end of treatment scan. T2\*-weighted gradient-echo planar images (EPI) will be acquired with the following parameters: TR = 1100ms, TE = 30ms, flip angle =  $65^\circ$ , matrix 64 x 64, field of view = 192mm, slice thickness = 3.0mm, with 48 slices to cover the entire brain.

**Statistical Analyses:** Baseline clinical and demographic characteristics will be collected and contrasts performed between treatment groups. Baseline characteristics found to be significantly associated with primary outcome measures will be included as covariates in the analyses. In general, less than 10% missing data have little impact on power and do not introduce bias, regardless of the missing data mechanism. If the percent missing data are greater than 10%, propensity score methods will be used for data imputation.

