For hypotheses 3A and 3B, the following preprocessing and analytical parameters will be used. Preprocessing: Post-acquisition preprocessing and statistical analysis of imaging data will be performed using FEAT (FMRI Expert Analysis Tool) Version 5.98, part of FSL (FMRIB's Software Library). Data will be preprocessed using scripting tools from FEAT. Non-brain signal will be removed using FSL's BET brain extraction. Scans will be corrected for motion using FSL's linear registration and scans will be spatially smoothed. Participants with head motion  $\geq 0.2$  mm will be excluded from the analyses (Power et al., 2012). Motion artifacts will be identified and scrubbed from each subject's data. Scans will be spatially co-registered with a standardized anatomical template (Montreal Neurological Institute) using a 12 parameter affine transformation. Analysis: Functional connectivity will be measured using a psychophysiological interaction (PPI) seed-based approach (Friston et al., 1997). PPI analysis is used to assess the functional coupling between different brain regions. The PPI is defined as the change in connectivity of one area (i.e., the seed region) to another in relation to the experimental context (e.g., alcohol vs. neutral cues). PPI analyses for resting state, trauma and alcohol/drug cues will be performed separately. Customized sq. wave forms representing the trauma run (1=trauma block and -1=neutral block) and the alcohol/drug cue run (1=alcohol/drug block and -1=neutral block) will be convolved with a double-gamma hemodynamic response function. A mask of the seed region will be made using a 12-mm diameter sphere located in the center of the AMY using the MNI coordinates (x, y, z =  $\pm 22, 0, -22$ ). The transformation parameters described above will also be applied to the mask. For each subject, the mean corrected and high pass filtered time series of the BOLD signal in the AMY will be extracted and used in a single subject whole brain PPI analysis. The PPI model will include the task vector, time series of the BOLD signal in the AMY, a term representing the positive task x seed interaction, and a term representing the negative task x seed interaction. The first level analysis will generate contrast images of the parameter estimates for each of the four regressors. Voxels will be thresholded at  $Z > 2.3$  using a corrected cluster threshold of  $p=0.05$ . The contrast images of the parameter estimates of the positive and negative task x seed interactions will be combined for group-level t-tests to identify regions that exhibited altered connectivity with the AMY during the trauma and alcohol/drug cues as compared to neutral cues. All group-level results will be thresholded at  $Z > 2.3$  using a corrected cluster threshold of  $p=0.05$ . Separate linear regression tests will be used to test for associations between PFC-AMY connectivity at baseline and improvement in AUD/SUD and PTSD symptoms during treatment. Changes in total standard drinks will be

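### Imaging power gives a per-group size of 26 as a total (52 are needed), no figure covers the Hypothesis 3 regression, and its resting predictor cannot be computed as written

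*Combined protocol and SAP*

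**What the plan says.** **Power.** The neuroimaging part of Power and Sample Size Estimation cites a study of 14 people with PTSD and 15 controls. It reports "The effect size for this difference was 0.8" (Cohen's d) and concludes that power "reaches .80 with a total sample size of" 26, two-tailed at .05. It then adds: "Another study of 45 cocaine-dependent individuals showed that lower PFC-AMY connectivity at baseline predicted relapse". That effect is given as 1.0, with N=34 for the same power and alpha. The Neuroimaging Component section sets the subset: "data will be acquired at baseline and end of treatment on a subset (n=40) of participants to examine" glutamate, resting connectivity and cue response.

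**Analysis.** The text for Hypotheses 3A and 3B regresses change in total standard drinks, or in CAPS-5, on baseline prefrontal-amygdala connectivity. The predictor is the centre-voxel estimate from each cluster with a significant task-by-seed interaction, both at rest and in response to cues. It states: "PPI analyses for resting state, trauma and alcohol/drug cues will be performed separately". It also states: "The PPI model will include the task vector", together with the amygdala time series and two interaction terms. The vectors it defines are: "Customized sq. wave forms representing the trauma run (1=trauma block and -1=neutral block) and the alcohol/drug cue run". In the resting runs, participants "keep their eyes opened and fixed on a cross-hair for two six-minute runs while resting state data are collected".

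**Covariates.** Baseline is named as a covariate for Hypotheses 1 and 2. For Hypothesis 3 neither baseline outcome nor arm is named. A general rule at the start of Statistical Analyses brings in baseline characteristics that are significantly associated with the primary outcomes.

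**The concern.** The two power sentences do not fit together: the smaller effect (0.8) is given the smaller sample (26), and the larger effect (1.0) the larger sample (34). At fixed power and alpha, the required sample must fall as the effect grows. Both figures are also sizes for a two-group comparison, whereas Hypothesis 3 is a regression on a continuous predictor. A reader therefore cannot tell what 40 scans can detect, and could not interpret a null result.

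The resting predictor raises a different problem. A psychophysiological interaction is a product of a task vector and a seed time series. Without a task there is no product. The resting half of 3A and 3B would then have its predictor settled during analysis.

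**Working it through.** **Inputs from the plan.** d=0.8 and d=1.0; two-sided alpha .05; power .80; stated totals 26 and 34; imaging subset 40. Groups are taken as equal in size (the cited study had 14 and 15).

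**Step 1: the plan's figures.** Two-sample t-test (noncentral t), solved for n per group:
- d=1.0: 16.7, so 17 per group and 2 × 17 = 34 in total. This reproduces the plan's 34.
- d=0.8: 25.5, so 26 per group and 2 × 26 = 52 in total. The plan gives 26 as the total.

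No other reading gives a total of 26 for d=0.8. The normal approximation gives 50, a one-sided t-test 42, a one-sided normal approximation 40, and a paired or one-sample test 15.

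**Step 2: power at the relevant totals.**

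| Effect | Total N | Power |
|---|---|---|
| 0.8 | 26 | 0.50 |
| 0.8 | 40 | 0.69 |
| 0.8 | 52 | 0.81 |
| 1.0 | 34 | 0.81 |
| 1.0 | 40 | 0.87 |

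**Step 3: the regression that is planned.** By Fisher's z, the smallest correlation detectable with 80% power, with k covariates, is r = tanh[(1.960 + 0.842) / √(n − 3 − k)].
- n=40, k=0: 2.802/√37 = 0.461, so r = 0.43.
- n=40, k=2: 2.802/√35 = 0.474, so r = 0.44.
- n=30, k=0: 2.802/√27 = 0.539, so r = 0.49.
- n=30, k=2: 2.802/√25 = 0.560, so r = 0.51.

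The 30 is an assumption. The plan excludes scans for head motion of 0.2 mm or more but gives no expected rate. All four values are per test, with no multiplicity adjustment. They assume a linear model, so they are only indicative for change in drink counts (3A).

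**Step 4: the resting predictor.** Setting the texts side by side:
- The interaction model needs a task vector.
- Vectors are defined for trauma against neutral and for alcohol/drug against neutral, coded 1 and −1.
- The resting runs contain fixation only and have no vector.
- The rest blocks inside the cue run do not help, because the vectors code only cue and neutral blocks.

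The resting interaction term therefore does not exist. The cue interactions are properly defined and are unaffected.

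**The case against.** **The 26 changes no decision.** This stands. The d=0.8 contrast is not run in this trial and does not set n=40. A reader might infer that the imaging subset should have been 52; the documents do not support that.

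**n=40 already covers the predictive effect.** The study behind d=1.0 concerns baseline connectivity predicting relapse, which is close to Hypothesis 3. With equal groups assumed, r = d/√(d² + 4) = 1/√5 = 0.45. At n=40 with two covariates, power for that r is about .82 if every scan is usable. So a reader should not infer that the subset is too small for the predictive effect cited. What remains is that the plan neither makes this conversion nor says what its regression can detect.

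**The resting fault has an evident reading.** The model already contains the amygdala time series as a regressor, and at rest that is the only computable term. This is fair, and it makes the repair easy. The text still asks for an interaction.

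**Covariates.** A reader might infer that leaving out baseline inflates false positives. The documents do not support this. Hypothesis 3 says only that connectivity will predict reduction, not that it will do so beyond baseline severity. If connectivity correlates c with baseline, baseline correlates ρ with week 8 (equal variances), and connectivity adds nothing further, its true correlation with change is −c√((1−ρ)/2). For c = .2 and .4 that is −.10 and −.20 at ρ=.5, and −.12 and −.24 at ρ=.3. Detecting such an association is a correct finding under the hypothesis as worded. The general covariate rule would also usually bring baseline in. Leaving out arm does not bias the slope, because the baseline scan precedes medication and arm is randomised.

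**Conclusion.** Two points hold on the text alone.

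1. The total of 26 for d=0.8 is half what is needed: 52, with power 0.50 at 26. It is a misstated supporting figure and not the basis of n=40. The 34 for d=1.0 should stay. No stated figure describes the Hypothesis 3 regression, which with 40 analysable scans detects a correlation of about 0.43 (0.44 with two covariates) at 80% power per test, and is less sensitive if scans are lost to motion.
2. The resting predictor in 3A and 3B cannot be computed as defined.

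Naming covariates for Hypothesis 3 is a design choice and its absence is not an error. The value of naming arm depends on the size of the treatment effect. In a simulation at n=40 with assumed values (connectivity slope .4, baseline-to-week-8 correlation .5, baseline already in the model), adding arm moves power from .86 to .85 at d=.2, the plan's own assumption for alcohol/substance severity. At d=1.27, its pilot PTSD effect, power moves from .65 to .85.

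**What to change.** 1. **Power and Sample Size Estimation.** Change the d=0.8 total to 52, or delete the sentence. Leave the N=34 sentence. Add: With 40 analysable scans, each Hypothesis 3 regression has 80% power (two-sided .05, per test, no multiplicity adjustment) for a correlation of about 0.43, or 0.44 with two covariates; sensitivity falls if scans are lost to motion.
2. **Hypotheses 3A and 3B, resting predictor.** Replace the interaction wording with whole-brain, seed-based functional connectivity of the amygdala time series already specified, at the same thresholds (Z > 2.3, cluster p = 0.05). Take the predictor from prefrontal clusters significantly connected with the seed. Leave the cue interaction analysis unchanged.
3. **Optional.** Name baseline outcome and arm as covariates in the Hypothesis 3 regressions, in place of the significance-triggered rule. Keep change as the outcome: a week-8 value is unclear for a drink total counted over a period.

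Items 1 and 2 cost wording only, with no new scans or participants. Item 3 costs two degrees of freedom per regression. If the 0.8 sentence is kept, its corrected total of 52 will exceed 40, so it should say that this contrast is not part of the trial.
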